1 SYNOPSIS

TITLE: DMIMT - Controlled, randomized, three-arm interventional study on safety and efficacy of regular respiratory muscle training in patients with myotonic dystrophy type 1
PROTOCOL-NUMBER: Version 1.2 (26. June 2019)
STUDY CENTRE/CLINIC/INSTITUE: Friedrich-Baur-Institute, Klinikum der Universität München, [name], Germany
OUTCOME MEASURE: The primary objective of this study is to investigate the safety of repetitive respiratory muscle training on respiratory muscle strength measured by MIP (maximum inspiratory pressure) in the upright position. The secondary objectives are 
• Efficacy and safety of repetitive inspiratory strength muscle training in 15 patients with myotonic dystrophy type 1,• Efficacy and safety of repetitive inspiratory endurance muscle training in 15 patients with myotonic dystrophy type 1,• Measurement of the effect on the quality of life and muscular performance in patients with myotonic dystrophy type 1 during respiratory muscle training or in patients without respiratory muscle training, measured using the questionnaires "DM1-Activ", "Respicheck" and "FDSS-Fatigue and Daytime Sleepiness-Scale".• Measurement of the influence on CO₂ and O₂ values in capillary blood gas analysis of patients with myotonic dystrophy type 1 during respiratory muscle training or in patients without respiratory muscle training.• Measurement of the impact of respiratory muscle training on the 6-minute walking test in patients with DM1.
METHODS: This is a monocentric, three-arm, controlled, randomized interventional study for patients with myotonic dystrophy type 1. The patient is not blinded regarding his therapy. The patient must provide informed consent prior to performing any protocol-related procedure. Eligible patients will be randomized and either perform 
(a) a nine-month respiratory strength training of respiratory muscles; or(b) a nine-month respiratory endurance training of the respiratory muscles, or(c) no respiratory muscle training. Lung function tests (FVC, FEV1, MIP, MEP), capillary blood gas analysis (pO ₂ , pCO ₂ , pH, Hb), 6-minute walking tests including oxygen saturation and patient questionnaires on quality of life and respiratory symptoms will be performed on scheduled visits throughout the treatment period. Adverse events (AEs) and concomitant medications / therapies are continuously monitored throughout the whole study period. Patients who are withdrawn from the trial for safety reasons or who withdraw their participation will not be replaced (i.e. a patient's study number will not be reused); however, it is planned to recruit additional patients if patients terminate participation prematurely.
NUMBER OF PATIENTS: A total of 45 patients are planned to be enrolled in the study. 15 patients per group will be randomized by the MUSCULAR IMPAIRMENT RATING SCALE (MIRS), age and gender.
INCLUSION- AND EXCLUSION CRITERIA: Inclusion criteria: A patient must meet all of the following criteria to be eligible for this study: 
1. the patient is willing and able to provide signed informed consent.2. the patient is ≥ 18 years old.3. the diagnosis of myotonic dystrophy type 1 has been confirmed by molecular genetics.

4. the patient is able and willing to perform pulmonary function tests (PFT) and blood sampling for capillary blood gas analysis (pO₂, pCO₂) throughout the study, to fill in a diary and to complete questionnaires.

Exclusion criteria:

A patient who meets one of the following criteria will be excluded from this study or not randomized to the study:

1. the patient requires invasive ventilation (non-invasive ventilation is allowed).
2. the patient uses non-invasive ventilation longer than 16h/day.
3. the patient participates in another clinical trial where therapy is provided.
4. the patient cannot perform pulmonary function tests (PFT).
5. the patient is diagnosed with central sleep apnea in polysomnography and not sufficiently treated by NIV ventilation.
6. the patient is diagnosed with obstructive sleep apnea and is not sufficiently treated with NIV ventilation.
7. the patient cannot meet the requirements of the study, according to the investigator.

STUDY PROCEDURES:

After provided consent to participate in the study, the following diagnostic procedures will be performed:

- At screening, the eligibility of the patient is evaluated and the allocation to one of the two treatment groups (1, 2) or the "placebo group" (3) without respiratory muscle training will be done.
- At baseline, all patients will be assessed for a respiratory function status with FVC, FEV1, MIP, MEP, capillary blood gas analysis, 6-minute walking test including oxygen saturation and questionnaires ("DM1-Activ", "Respicheck" and "FDSS-Fatigue and Daytime Sleepiness-Scale") as well as a clinical examination (including MIRS).
- Patients of the groups 1 and 2
 - will perform a respiratory muscle training (IMT, inspiratory muscle training) for nine months.
 - During training (between months 3 and 9), inspiratory resistance will be increased at each visit (10-20% of baseline MIP), measured by the Borg scale.
 - Patients will be asked fill in a diary about their performed respiratory muscle training
- Patients of group 3 will not perform respiratory muscle training.
- At every visit, all patients will perform the following assessments every two months:
 - Pulmonary function tests, including FVC, FEV1, MIP, MEP (6 times including screening visit)
 - Functional assessments (6-minute walk test + Borg scale at screening, month 1, month 5 and month 9).
 - Clinical examination including MIRS at screening and month 9.
 - Patients are asked to complete the following questionnaires at defined times: three questionnaires on health status in myotonic dystrophy type 1, effects of fatigue and daytime fatigue on everyday life and one questionnaire on clinical symptoms of respiratory insufficiency (DM1-ACTIV, FDSS - FATIGUE AND DAYTIME SLEEPINESS SCALE und RESPICHECK).

STATISTICAL METHODS:

All patients who participate in this study will be included in the analysis. Data collected in this study will be documented using summary tables, figures, and patient data listings. For continuous variables, descriptive statistics (n, mean, median, standard deviation, minimum, and maximum) will be presented. For categorical variables, frequencies and percentages will be presented. Graphical displays will be presented as appropriate.

Power and Sample Size:

This is an exploratory study about efficacy and safety of respiratory muscle training in patients with Myotonic Dystrophy Type 1 and is not powered to make other statistical inferences.

Analysis-Sets:

Full Analysis Set: This analysis set consists of all patients who performed respiratory muscle therapy for at least 9 months or who did the check-ups throughout the 9 months without respiratory muscle training. All analyses will be based on this analysis set

Demographics and Baseline Characteristics:

Demographic and baseline data on medical/surgical history and disease history including length of repeats will be summarized using descriptive statistics for continuous variables and frequency distribution for categorical variables.

Safety:

A deterioration of >15% of FVC in comparison with baseline measurements will be defined as an AE, as well as developing unusual myalgia of respiratory muscles for more than 12 hours. The Adverse events will be collected from enrollment (=signed informed consent) through month 9 plus 7 days. Adverse events will be coded using the Medical Dictionary for Regulatory Activities, and categorized by system organ class and preferred term. All AEs will be displayed in patient listings. Adverse events will be categorized and tabulated for the treatment group overall by severity, seriousness, and relationship to study treatment

Efficacy:

Observed measurements and changes from baseline to each study time point in respiratory function parameters (% predicated sitting and supine FVC, forced expiratory volume in the 1st second of the FVC maneuver [FEV1], maximal inspiratory pressure [MIP], maximal expiratory pressure [MEP], and peak expiratory flow [PEF]); and blood gas analysis (pH, pCO₂, pO₂) as well as oxygen saturation and six-minute-walk-test with Borg scale will be summarized using descriptive statistics. In addition, 95% confidence intervals will be used to estimate the change from baseline at each study visit. Graphical displays showing data over time will be presented as appropriate.

REFERENCE TREATMENT:

There is no reference treatment to respiratory muscle training.

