8.3.3 Pulmonary Function Testing

PFT will be performed at time points specified in Appendix A. The PFT administration protocol will be standardized in accordance with the American Thoracic Society (ATS) guidelines (American Thoracic Society/European Respiratory 2002). PFT will include the assessment of

forced vital capacity (FVC), forced expiratory volume in the 1st second of the FVC maneuver (FEV1), maximal inspiratory pressure (MIP), maximal expiratory pressure (MEP), and peak expiratory flow (PEF) in the upright and supine positions.

FVC is the maximal volume of gas that can be exhaled with the patient breathing forcefully to obtain maximal airflow rates. For this measurement, the patient is instructed to inspire completely until the lungs are fully inflated. A nose clip is used to prevent leakage. Then the patient exhales as far as possible until the lungs are almost empty and the measured volume is recorded. Data are reported in liters and percent of predicted normal values based on age, gender, race, and height (Hankinson, Odencrantz et al. 1999).

Respiratory status will be assessed by spirometry using the KoKo PFT System © 2010 nSpire Health Inc. spirometer. FVC and FEV1 will both be measured in upright and supine position. In addition, the function of the respiratory muscles will be evaluated by the maximal respiratory pressures MIP for maximum inspiratory pressure and MEP for maximum expiratory pressure. For MIP and MEP in upright position, the CareFusion digital manometer from microRPM™ will be used with a flanged mouthpiece, as recommended by the American Thoracic Society (ATS) (American Thoracic Society/European Respiratory 2002). Calibration of software and spirometry devices will be done daily, as described in software manuals (Bolliger, Mathur et al. 2002).

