8.3.6 Clinical Laboratory Tests (blood analysis)

At the initial examination and every two months a capillary blood analysis will be performed, using epoc blood analysis system, which consists of epoc® BGEM Test Card, epoc® Host2 Mobile Computer and epoc® Care-FillTM Capillary Tubes. Calibration will be done as recommended in users' manual. The Care-Fill™ Capillary Tubes are designed to collect a blood sample from a skin puncture. The tube fills with a blood sample through a combination of capillary action and gravity flow. When sufficient blood is present, the tube fills readily and preserves the integrity of the blood sample until it can be tested by preventing clotting and alteration of analytic concentrations. For each blood draw, approx. 90µl are needed for sufficient analysis. In total, approx. 540µl are drawn per patient during the whole study. The following parameters will be measured: pH, pCO2, pO2.

Observed measurements and changes from baseline to study time points in month 1,3,5,7 and 9 will be descriptively summarized. All laboratory values will be classified as normal, above normal, or below normal based on normal ranges provided by the laboratory. Frequencies of abnormal values and clinically significant abnormal values will be summarized. All data will be presented in listings along with individual listings of patients with clinically significant abnormal laboratory values.

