9 ADVERSE EVENTS REPORTING (AE)

A deterioration of >15% of FVC in comparison to baseline measurements will be defined as an AE, as well as developing unusual myalgia of respiratory muscles for more than 12 hours. AEs and SAEs will be coded using the Medical Dictionary for Regulatory Activities and summarized by primary system organ class and preferred term. Detailed listings of patients who experience AEs or SAEs will be presented. The incidence of treatment-emergent AEs and SAEs will be tabulated (frequencies and percentages) by severity, and by relationship to treatment. Adverse event severity will be categorized as mild, moderate, or severe. In tabulating severity of AEs on a per patient basis, the greatest severity will be assigned to a patient should there be more than one occurrence of the same AE with different reported severities. Relationships of the AE to treatment will be categorized as not related, unlikely related, possibly related, or related. The highest level of association will be reported in patients with differing relationships

for the same AE. Listings of AEs and SAEs for all patients will be provided, which will include severity and relationship to treatment, as well as actions taken regarding treatment, and patient outcome. A separate listing for patients who withdraw from the study due to AEs will be provided. The incidence of AEs leading to study discontinuations will also be summarized.

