11.6 Clinical Study Report

A final clinical study report will be produced after study completion.

12 APPENDIX A: Schedule(s) of Study Events

Group 1 and 2:

	Visit 1 Screening month 0	Visit 2 follow-up month 1	Visit 3 follow-up month 3	Visit 4 follow-up month 5	Visit 5 follow-up month 7	Visit 6 final examination month 9
Informed consent	x					
Randomization	x					
Clinical examination including MIRS (Muscular Impairment Rating Scale)	x					x
Pulmonary function test (PFT), sitting and supine	x	x	x	x	x	x
Collection of historical data, especially polysonography and lung function	x					
Maximal expiratory pressure (MEP)	x	x	x	x	x	x
Maximal inspiratory pressure (MIP)	x	x	x	x	x	x
Blood gas analysis (capillary: pO ₂ , pCO ₂ , pH, Hb)	x	x	x	x	x	x
6-minute-walk-test including BORG-scale prior to and after test	x	x		x		x
questionnaire DM1-Activ	x	x	x	x	x	x
questionnaire FDSS (fatigue and daytime sleepiness)	x	x	x	x	x	x
questionnaire "Respicheck" for respiratory insufficiency	x	x	x	x	x	x
Check of patient diary		x	x	x	x	x
Check of data of respiratory training (Respifit S -training device)		x	x	x	x	x
adverse events (AE)		x	x	x	x	x
Instructions for the use of the training device	x	x	x	x	x	x
Increase of resistance by 10%-20%, individually according to BORG scale	start: 30% of MIP	x	x	x	x	

Group 3:

	Visit 1 Screening month 0	Visit 2 follow-up month 1	Visit 3 follow-up month 3	Visit 4 follow-up month 5	Visit 5 follow-up month 7	Visit 6 final examination month 9
Informed consent	X					
Randomization	X					
Clinical examination including MIRS (Muscular Impairment Rating Scale)	X					X
Collection of historical data, especially polysomnography and lung function	X					
Pulmonary function test (PFT), sitting and supine	X			X		X
Maximal expiratory pressure (MEP)	X			X		X
Maximal inspiratory pressure (MIP)	X			X		X
Blood gas analysis (capillary: pO ₂ , pCO ₂ , pH, Hb)	X			X		X
6-minute-walk-test including BORG-scale prior to and after test	X			X		X
questionnaire DM1-Activ	X			X		X
questionnaire FDSS (fatigue and daytime sleepiness)	X			X		X
questionnaire "Respicheck" for respiratory insufficiency	X			X		X
Check of patient diary						
Check of data of respiratory training (Respifit S -training device)						
adverse events (AE)		X	X	X	X	X
Instructions for the use of the training device						
Increase of resistance by 10%-20%, individually according to BORG scale						

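### The synopsis gives every patient six lung function visits, but Appendix A gives controls three, so the FVC-fall adverse event has five chances of detection in each training arm and two in control

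*Protocol*

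**What the plan says.** **Synopsis, Study Procedures.** Straight after the line on Group 3, the text continues "At every visit, all patients will perform the following assessments every two months". The list beneath includes "Pulmonary function tests, including FVC, FEV1, MIP, MEP (6 times including screening visit" and "6-minute walk test + Borg scale at screening, month 1, month 5 and month 9". No arm is exempted.

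**Section 8.3.6.** Capillary blood gas is taken at the initial examination and every two months, at about 90 µl per draw. About 540 µl "are drawn per patient during the whole study". For the analysis, "Observed measurements and changes from baseline to study time points in month 1,3,5,7 and 9 will be descriptively summarized". No arm is exempted here either.

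**Section 8.3.3.** "PFT will be performed at time points specified in Appendix A".

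**Section 12, Appendix A.** Each of the two tables has a row "Pulmonary function test (PFT), sitting and supine". For Groups 1 and 2 it is marked at months 0, 1, 3, 5, 7 and 9. For Group 3 it is marked at months 0, 5 and 9. In Group 3 the rows for MIP, MEP, blood gas, walk test and all three questionnaires carry the same three marks, while the adverse event row is marked at months 1, 3, 5, 7 and 9.

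**Sections 7.2.1, 8.4 and 9.** Routine safety assessments are the primary endpoints, and pulmonary function is one of the safety parameters. Section 9 adds: "A deterioration of >15% of FVC in comparison to baseline measurements will be defined as an AE".

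**The concern.** There are two linked problems.

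The first is a plain contradiction. Staff working from the synopsis and staff working from Appendix A would run different control arms.

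The second follows if Appendix A is used. An FVC fall above 15% can be recorded only when spirometry is done. Controls are asked about adverse events at months 1, 3 and 7 but have no scheduled spirometry then. The training arms do. The event is counted as a cumulative incidence, so the arms that are measured more often will tend to show more of it even if training does nothing. A reader comparing arms on the primary safety endpoint could take this difference in detection for harm from training. No passage restricts the event to visits that all arms share.

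**Working it through.** **1. Visit counts and the protocol's own figure**

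| Source | Tests per control patient | Post-baseline |
|---|---|---|
| Synopsis, lung function | 6 | 5 |
| 8.3.6, blood gas | 540 / 90 = 6 | 5 (months 1, 3, 5, 7, 9) |
| Appendix A, Group 3, both tests | 3 (months 0, 5, 9) | 2 |

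The 540 µl figure is reproduced as 6 × 90. Under the Group 3 table it would be 3 × 90 = 270 µl. The synopsis also gives all patients a month-1 walk test, which the Group 3 table lacks.

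**2. Direction of the imbalance**

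Months 5 and 9 are a subset of months 1, 3, 5, 7 and 9. With the same true FVC course in every arm, the chance of at least one recorded fall over five visits cannot be smaller than over two. This needs no numerical assumption.

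**3. Size, independent transient falls (assumed)**

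Let p be the chance of a recorded fall at any one visit. The documents do not give it. The chance of at least one fall over k visits is 1 − (1 − p)^k. Patient counts are that chance × 15.

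| p | 5 visits | 2 visits | Patients per 15 | Ratio |
|---|---|---|---|---|
| 2% | 9.6% | 4.0% | 1.4 vs 0.6 | 2.4 |
| 5% | 22.6% | 9.8% | 3.4 vs 1.5 | 2.3 |
| 10% | 41.0% | 19.0% | 6.1 vs 2.9 | 2.2 |

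**4. Size, allowing for the shared baseline**

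All changes are taken from one measured baseline. With equal measurement error at each test and no true change, any two changes have correlation 0.5. With c the normal quantile of p, the chance becomes 1 − ∫ φ(z) [1 − Φ((c − √0.5·z)/√0.5)]^k dz.

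| p | 5 visits | 2 visits | Ratio |
|---|---|---|---|
| 2% | 7.5% | 3.7% | 2.0 |
| 5% | 16.6% | 8.8% | 1.9 |
| 10% | 29.2% | 16.8% | 1.7 |

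**5. Size, gradual lasting change (assumed)**

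Each patient is given a linear change over nine months, in percent of baseline, plus independent measurement error at baseline and at each visit. An event is any measured change below −15%. Ratios are five visits to two, by simulation.

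| Mean, SD of 9-month change | Error SD 0 | 2 | 3 | 4 | 5 |
|---|---|---|---|---|---|
| −5, 8 | 1.00 | 1.03 | 1.09 | 1.17 | 1.25 |
| −2, 4 | 1.00 | 1.06–1.07 | 1.24–1.26 | 1.45 | 1.56–1.59 |

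Where two values are shown, they depend on whether the change is divided by the true or the measured baseline. In both models the excess stays below one patient per 15. The largest is about 0.75, at mean −5, SD 8 and error SD 5.

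**6. With equal visits**

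If all arms have the same visits (5 and 5, or 2 and 2), the ratio is 1.0 in every model.

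**The case against.** - **Appendix A governs.** Section 8.3.3 defers to it, and a separate, consistent Group 3 table looks intended. The synopsis lead-in is loose anyway: it says every visit, then lists the walk test at four. This stands as a guide to which schedule staff would follow for lung function. It does not remove the conflict over six tests, and it leaves the five-to-two count in place.
- **Section 8.3.6 concerns blood gas only.** This is correct. The lung function contradiction rests on the synopsis, and 8.3.6 shows the same conflict for blood gas.
- **No between-arm comparison of this event is specified.** Section 10.1 plans no formal tests, and the synopsis tabulates adverse events for the treatment group overall. The harm is therefore one of interpretation, not of an error rate. A controlled, randomised trial with safety as primary endpoint will nevertheless be read by arm.
- **Closer monitoring of trained patients has a reason.** At months 1, 3 and 7 they have device checks and resistance increases, which controls do not. Unequal monitoring may be deliberate. The difficulty lies in counting a measurement-defined event over unequal visits.
- **The size is assumed.** Independent visits are an upper case, and the gradual-change models give less than one extra patient per arm. This stands, so only the direction and the visit counts can be stated firmly.

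**Conclusion.** The concern holds. The contradiction between the synopsis, section 8.3.6 and Appendix A is explicit and needs no assumption. Under Appendix A the FVC-fall adverse event has five scheduled chances of detection in each training arm and two in control, and the resulting bias can only make training look worse.

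Its size is not fixed by the documents. Under the assumptions shown, the incidence ratio with no training effect lies between 1.0 and 2.4. It is near the top for short-lived falls that are independent between visits and near the bottom for lasting falls measured with little error.

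The effect is limited to one adverse event type in a descriptive analysis. Respiratory myalgia, the other defined event, does not depend on spirometry, and mean changes summarised visit by visit are not distorted. The point should be fixed, though it does not undermine the trial as a whole.

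**What to change.** Reconcile the synopsis, section 8.3.6 and Appendix A so that one visit schedule is stated for Group 3. Which schedule is meant is for the sponsor to say.

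- **If Appendix A stands:** correct the test counts and walk-test months in the synopsis, and the blood volume and summary months in 8.3.6. State that the between-arm incidence of the FVC-fall event uses months 5 and 9 only. List falls seen only at months 1, 3 or 7 in the training arms separately. The cost is a text correction and one tabulation rule. The drawback is that early falls under training leave the comparison, though they remain in the listings and safety reporting.
- **If the synopsis schedule is meant:** correct the Group 3 table so that all arms share the same lung function visits, and use all visits for this event. The cost is three more test sessions per control patient. Appendix A marks only an adverse event check in those months and does not say whether it is done on site, so these may be new clinic visits.

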7.2 End Points

7.2.1 Safety end points

Routine safety assessments are considered as primary endpoints of this study and are described in the sections 8, 9, 10 and 11.

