8.4 Safety Assessments

Safety will be assessed for all enrolled patients from the time of signing the informed consent up to 7 days after the final study visit (month 9). Safety parameters include pulmonary function testing (PFT, including FVC, FEV1, MIP, MEP), physical examination, vital signs and –at decision of investigator- clinical laboratory tests as needed. See also Section 9.

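### The synopsis calls a nine-month completer set the Full Analysis Set and bases every analysis on it, so patients who stop training for an adverse event can drop out of the primary safety tables

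*Protocol*

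**What the plan says.** The Statistical Methods part of the protocol synopsis opens with "All patients who participate in this study will be included in the analysis". A few lines later it defines a single set, the Full Analysis Set. A patient enters it in one of two ways: as one of "all patients who performed respiratory muscle therapy for at least 9 months", or by attending the check-ups throughout nine months without training. It then states: "All analyses will be based on this analysis set". The protocol defines no separate safety set.

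Other text bears on who is analysed:

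- Section 7.2.1: "Routine safety assessments are considered as primary endpoints of this study".
- Section 8.4: "Safety will be assessed for all enrolled patients", from consent until seven days after the month 9 visit. The synopsis sets the same collection window: "The Adverse events will be collected from enrollment (=signed informed consent) through month 9 plus 7 days".
- Section 9: "The incidence of AEs leading to study discontinuations will also be summarized". AE listings are promised for all patients, with a separate listing of those who withdraw because of an AE.
- Synopsis, Safety: "Adverse events will be categorized and tabulated for the treatment group overall by severity".
- Section 7.6 names an AE the patient cannot tolerate as a possible reason to end training. It adds that ending training need not mean leaving the study, and that such a patient may be admitted to the control group.
- Section 7.2.3 counts a patient as completed once the month 9 visit has taken place.
- The synopsis and Sections 7, 7.2.4 and 7.6 provide for recruiting extra patients to make up for those who leave early.

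**The concern.** A full analysis set normally keeps everyone who was randomised. This one keeps only those who trained to the end, or controls who attended to the end, and it is the stated basis for every analysis, including the primary safety analysis. A patient whose training ends because of an AE is the patient a safety study most needs to count. Under the synopsis rule that patient leaves both the numerator and the denominator of the AE tables.

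The set is also narrower than study completion. A patient who stops training because of an AE but attends every visit to month 9 is a completer under Section 7.2.3 and has full data. Read literally, that patient has neither trained for nine months nor gone nine months without training, and so meets neither part of the definition.

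Top-up recruitment makes the loss harder to see: an arm can again show 15 completers although more than 15 patients were exposed. Efficacy means could be biased too, but only if stopping is related to outcome.

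**Working it through.** **1. The statements side by side.**

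| Place | Who is counted |
|---|---|
| Synopsis, Statistical Methods, first sentence | All participants |
| Synopsis, Analysis-Sets | Nine-month trainers and nine-month untrained attenders, for all analyses |
| Section 8.4 | All enrolled patients (safety assessment) |
| Section 9 | Patients who discontinue because of an AE need their own incidence |
| Section 10.4 | All enrolled patients, but only for accountability |

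The first two rows cannot both hold. In a completer set, the incidence in the fourth row is essentially zero by construction. Section 10 has no analysis-set definition that would override the synopsis.

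**2. AE incidence: an illustration on assumed counts.** The protocol states 15 patients per arm and no AE or dropout rate. Assume k patients per training arm stop for an AE and no completer has one.

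- With top-up to 15 completers: all patients k/(15 + k), completer set 0/15.
- Without top-up: all patients k/15, completer set 0/(15 − k).
- Both training arms pooled, with top-up: all patients 2k/(30 + 2k), completer set 0/30. This applies if the synopsis's overall treatment group means the two training arms together.

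Intervals are exact (Clopper-Pearson) 95%. For zero events the upper limit is 1 − 0.025^(1/n), which gives 21.8% for n = 15 and 11.6% for n = 30.

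| k | One arm, top-up: all vs completers | One arm, no top-up: all vs completers | Pooled, top-up: all vs completers |
|---|---|---|---|
| 1 | 1/16 = 6.3% (0.2–30.2) vs 0/15 (0–21.8) | 1/15 = 6.7% (0.2–31.9) vs 0/14 (0–23.2) | 2/32 = 6.3% (0.8–20.8) vs 0/30 (0–11.6) |
| 2 | 2/17 = 11.8% (1.5–36.4) vs 0/15 (0–21.8) | 2/15 = 13.3% (1.7–40.5) vs 0/13 (0–24.7) | 4/34 = 11.8% (3.3–27.5) vs 0/30 (0–11.6) |
| 3 | 3/18 = 16.7% (3.6–41.4) vs 0/15 (0–21.8) | 3/15 = 20.0% (4.3–48.1) vs 0/12 (0–26.5) | 6/36 = 16.7% (6.4–32.8) vs 0/30 (0–11.6) |

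**3. A milder case, with AEs among completers too.** In one arm of 15, four patients have an AE and three of them stop: 4/15 = 26.7% (7.8–55.1) in all patients, against 1/12 = 8.3% (0.2–38.5) in completers. Over both arms, six of 30 have an AE and four of them stop: 6/30 = 20.0% (7.7–38.6) against 2/26 = 7.7% (0.9–25.1).

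**4. How likely is it that anyone is affected?** With an assumed probability q that a trained patient stops for an AE, the chance of at least one among n is 1 − (1 − q)^n. For q = 5%, 10% and 20% this is 53.7%, 79.4% and 96.5% with n = 15, and 78.5%, 95.8% and 99.9% with n = 30.

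**5. Efficacy means.** Under normality, if the worst 1 of 16, 2 of 17 or 3 of 18 are lost, the expected mean change of the remaining 15 rises by 0.12, 0.21 or 0.28 SD. If the tendency to drop out correlates 0.5 with outcome, the shift is half that: 0.06, 0.10 or 0.14 SD. If dropout is unrelated to outcome, it is 0.

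**The case against.** The protocol body leans towards using everyone. Section 10 carries no completer restriction, Section 7.9 says incomplete training will be considered, and Section 10.8 analyses data as collected. If the body governs, no patient is lost. This is true, but no text says that it governs, and the synopsis sentence is explicit. Some of this support is also indirect: Section 8.4 is about who is assessed, and Section 10.8 is about imputation. The firm conflicts are with the synopsis's own first sentence and with Section 9.

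A patient who stops training and is admitted to the control group could be read into the second part of the definition. That reading is possible but strained, since the patient did train. It would also swap exclusion for another error, by counting a training-arm patient as a control.

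AEs are not hidden altogether. All of them appear in patient listings, and Section 9 lists AE withdrawals separately. This stands: the damage is to tabulated incidences and their denominators.

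The table in step 2 assumes no AE among completers, although the protocol counts prolonged respiratory myalgia as an AE and names myalgia as a training risk. That is fair, and step 3 shows the smaller relative distortion. The single-arm intervals overlap widely. In the pooled case with k = 2 the completer upper limit falls only just short of the all-patient rate (11.6% against 11.8%).

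Finally, the study is exploratory and has no formal tests. That does not remove the need for an unselected denominator, because descriptive AE incidences are its main safety output.

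**Conclusion.** The concern holds. The synopsis contradicts itself and Section 9 on the population for the primary endpoint, and its explicit rule takes patients who stop for an AE out of the safety tables, even when their follow-up is complete. This is an error in the protocol's own text, not a detail left to an analysis plan.

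The protocol gives no rate from which to compute the size. On the assumed counts of one to three AE stoppers per arm, an incidence of about 6% to 20% would be shown as zero. With AEs among completers as well, 26.7% would be shown as 8.3%. If nobody stops for an AE, no AE is lost. Efficacy bias is secondary and depends wholly on whether dropout is related to outcome. The correction should be made before results are known, because the choice between the two readings affects how safe the training appears.

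**What to change.** Rewrite the Analysis-Sets paragraph of the synopsis and reconcile it with Sections 8.4 and 9:

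1. **Safety set:** all randomised patients by assigned arm, including those who end early, with all AE data collected. Because collection starts at consent, list separately any AE in a patient who consented but was not randomised.
2. **Full Analysis Set:** all randomised patients in their randomised arm, using all observed data without imputation, in line with Section 10.8. Patients who stop training, or who are admitted to the control group under Section 7.6, stay in their randomised arm for analysis. Patients recruited to make up for dropouts are added and do not displace those who stopped.
3. **Completer set:** the present definition under this name, for sensitivity analysis only.

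The cost is one reworded paragraph, with no change to visits or data collection. The safety result may look slightly less favourable. Data from early leavers may be incomplete, since Section 7.2.4 asks for discontinuation assessments only where possible; the report should state how many are missing.
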